Blood pressure will be monitored during L-NMMA infusions. At each L-NMMA infusion, blood pressure will be measured before infusion, 1 hour (± 15 minutes) after infusion start, and at infusion completion. Automatic blood pressure readings will be performed unless manual reading is needed. If systolic blood pressure is >180 mmHg at the 1-hour (± 15 minutes) check, stop the infusion and recheck blood pressure after 15–30 minutes. If blood pressure is not <160 mmHg, recheck blood pressure after another 15–30 minutes. If blood pressure is still not <160 mmHg, the subject is to be discontinued from the trial. The infusion can be resumed in subjects whose blood pressure lowers to <160 mmHg at the first or second recheck. If systolic blood pressure again increases beyond 180 mmHg, the infusion should be stopped and the subject is to be discontinued from the trial. If systolic blood pressure is >180 mmHg at infusion completion, recheck blood pressure after 15–30 minutes. If blood pressure is not <160 mmHg, recheck blood pressure after another 15–30 minutes. If blood pressure is still not <160 mmHg, the subject is to be discontinued from the trial.

Subjects whose treatment is interrupted or permanently discontinued due to an AE including abnormal laboratory value must be followed at least once a week for 4 weeks and subsequently at 4-week intervals until resolution of the event to Grade 1 or better. Dose interruptions should be reported on the appropriate Dosage Administration case report form (CRF). Any AE during Cycle 1 that delays administration of Cycle 2 by more than 7 days will be considered a DLT (see Section 8.0 — Statistical Considerations). The maximum time allowed for toxicity-related treatment interruption for all subsequent cycles is 3 weeks from the intended dosing day. If interruption is > 3 weeks, the subject must be discontinued from the trial treatment. However, the subject will continue to be followed for toxicity.

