5.6 Subject Withdrawal/Discontinuation Criteria

Subjects may withdraw consent at any time for any reason or be dropped from the trial at the discretion of the investigator should any untoward effect occur. In addition, a subject may be withdrawn by the investigator or Sponsor if enrollment into the trial is inappropriate, the trial plan is violated, or for administrative and/or other safety reasons. Specific details regarding discontinuation or withdrawal are provided in Section 7.1.4 — Other Procedures.

A subject must be discontinued from the trial for any of the following reasons:

- The subject or legal representative (such as a parent or legal guardian) withdraws consent
- Confirmed radiographic disease progression
- Any AE during Cycle 1 that delays administration of Cycle 2 by more than 7 days or dose interruption that exceeds 21 days in subsequent cycles
- Unacceptable adverse experiences
- Any \geq Grade 4 AE
- Severe (Grade 3) or life-threatening (Grade 4) immune-mediated complication
- Intercurrent illness that prevents further treatment administration
- Investigator's decision to withdraw the subject
- The subject has a confirmed positive serum pregnancy test
- Noncompliance with trial treatment or procedure requirements
- The subject is lost to follow-up
- Death
- Administrative reasons
- Subjects whose blood pressure is >180 during or after L-NMMA infusion and does not return to <160 mmHg after 2 rechecks spaced 15–30 minutes apart

The end of treatment (EOT) and follow-up visit procedures are listed in Section 6.0 (Trial Flow Chart) and 7.1.4.2 (Visit Requirements). At EOT, each subject will be followed for 30 days for AE monitoring (SAEs will be collected for 90 days after EOT as described in Section 7.2.3.1).

Subjects who discontinue for reasons other than progressive disease (PD) will have post-treatment follow-up for disease status until disease progression, initiating a non-study cancer treatment, withdrawing consent, or becoming lost to follow-up.

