7.2 Assessing and Recording AEs

An AE is defined as any untoward medical occurrence in a patient or clinical investigation subject administered a pharmaceutical product and which does not necessarily have to have a causal relationship with this treatment. An AE can, therefore, be any unfavorable and unintended sign (e.g., abnormal laboratory finding), symptom, or disease temporally associated with the use of a medicinal product or protocol-specified procedure, whether or not considered related to the medicinal product or protocol-specified procedure. Any worsening (i.e., any clinically significant adverse change in frequency and/or intensity) of a preexisting condition that is temporally associated with the trial treatment is also an AE. Progression of the cancer under study is not considered an AE.

From the time of informed consent signing through 30 days following cessation of treatment, all AEs must be reported by the investigator. AE reporting will be performed according to 21 CFR 312.32. AEs will be recorded at each examination on the Adverse Event CRFs. AEs (including lab abnormalities that constitute AEs) should be described using a diagnosis whenever possible, rather than individual underlying signs and symptoms. When a clear diagnosis cannot be identified, each sign or symptom should be reported as a separate AE. Conditions that were already present at the time of informed consent should be recorded in the Medical History page of the subject's CRF. The reporting timeframe for AEs meeting any serious criteria is described in section 7.2.3.1. The investigator will make every attempt to follow all subjects with non-SAEs for outcome.

AEs will not be collected for subjects during the prescreening period as long as that subject has not undergone any protocol-specified procedure or intervention. If the subject requires a

blood draw, fresh tumor biopsy etc., the subject is first required to provide consent to the main study and AEs will be captured according to guidelines for standard AE reporting.

The occurrence of AEs should be sought by non-directive questioning of the subject at each study visit. AEs may also be detected when they are volunteered by the subject during or between visits or through physical examination, laboratory test, or other assessments. As far as possible, each AE should be evaluated to determine:

1. Severity grade (CTCAE Grade 1–4)
2. Duration (start and end dates or if continuing at the safety follow-up visit)

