3. Relationship to the study treatment (reasonable possibility that AE is related: no, yes)
4. Action taken with respect to trial treatment (none, dose adjusted, temporarily interrupted, permanently discontinued, hospitalized, unknown, not applicable)
5. Whether medication or therapy was given (no concomitant medication/non-drug therapy, concomitant medication/non-drug therapy)
6. Outcome (not recovered/not resolved, recovered/resolved, recovering/resolving, recovered/resolved with sequelae, fatal, unknown)
7. Whether it is serious, where a SAE is defined as in Section 7.2.3.1.

All AEs should be treated appropriately. Such treatment may include changes in trial treatment including possible interruption or discontinuation, starting or stopping concomitant treatments, changes in the frequency or nature of assessments, hospitalization, or any other medically required intervention. Once an AE is detected, it should be followed until its resolution, and assessment should be made at each visit (or more frequently, if necessary) of any changes in severity, the suspected relationship to the trial treatment, the interventions required to treat it, and the outcome.

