8.0 STATISTICAL CONSIDERATIONS

This is a Phase Ib trial investigating the use of L-NMMA in combination with pembrolizumab in subjects with melanoma, NSCLC, HNSCC, cHL, urothelial carcinoma, cervical cancer, esophageal cancer, gastric cancer, hepatocellular carcinoma, merkel cell carcinoma, primary mediastinal large B-cell lymphoma, renal cell carcinoma, small cell lung cancer, MSI-H/dMMR cancer or for the treatment of adult patients with unresectable or metastatic tumor

mutational burden-high (TMB-H) [≥ 10 mutations/megabase (mut/Mb)] solid tumors. The study is designed to determine the DLTs and MTD of the L-NMMA plus pembrolizumab combination. DLT will be defined as any treatment-related death or any \geq Grade 3 AE (NCI CTCAE v4.03) unless there is clear alternative evidence that the AE was not caused by the trial treatment. DLT will also include any AE during Cycle 1 that delays administration of Cycle 2 by more than 7 days:

- Grade 4 neutropenia ($ANC < 500/mm^3$) lasting ≥ 7 days
- Grade 3 febrile neutropenia lasting > 24 hours (single temperature of $> 38.3^\circ C$ or a sustained temperature of $> 38^\circ C$ for > 1 hour (non-axillary) with $ANC < 1000/mm^3$)
- Grade 4 febrile neutropenia of any duration
- Grade 4 thrombocytopenia (platelets $< 25,000/mm^3$) or Grade 3 thrombocytopenia with significant bleeding
- Hematological toxicities can be managed for a period that will not exceed more than 7 days. In the event that the hematological toxicity persists for more than the allowed time, it will be considered a DLT
- Grade 3–4 elevation in ALT or AST associated with a Grade 2 elevation in bilirubin that is at least possibly related to study drug (Hy's Law)
- Any \geq Grade 3 electrolyte abnormality considered clinically significant or which lasts ≥ 72 hours
- Grade 3 infusion-related reactions that recur despite appropriate medical management
- Any other treatment-related \geq Grade 3 non-hematological AE except hyperlipidemia in subjects not receiving maximum medical management or electrolyte abnormalities that may be managed with supplements

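### The Cycle 2 delay criterion has no attribution exception, so AEs clearly unrelated to treatment can be scored as DLTs; this pushes dose selection downward, by an amount that depends on a rate the documents do not give

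*Combined protocol and SAP*

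**What the plan says.** Section 8.0 defines a DLT in two sentences. The first covers treatment-related death and Grade 3 or higher AEs, "unless there is clear alternative evidence that the AE was not caused by the trial treatment". The second adds a further route: "DLT will also include any AE during Cycle 1 that delays administration of Cycle 2 by more than 7 days". It has no grade threshold and no attribution condition. It ends in a colon and is followed by a list of specific toxicities.

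Section 5.2.1.2 states the rule again as a complete sentence with no list: "Any AE during Cycle 1 that delays administration of Cycle 2 by more than 7 days will be considered a DLT". Section 5.6 uses the same opening for mandatory discontinuation: "Any AE during Cycle 1 that delays administration of Cycle 2 by more than 7 days or dose interruption that exceeds 21 days" in later cycles.

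Section 3.1 (primary endpoint) gives only the base definition with its exception and refers to Section 8.0 for the detail.

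Section 7.2 defines an AE as an event "which does not necessarily have to have a causal relationship with this treatment". The exclusion that bears on this point is "Progression of the cancer under study is not considered an AE". The same section has the investigator record, for each AE, "Relationship to the study treatment (reasonable possibility that AE is related: no, yes".

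**The concern.** A DLT is the only outcome the CRM learns from, and it is meant to measure toxicity that varies with the L-NMMA dose. The delay route admits events with no link to dose. Four unrelated events show the inconsistency:

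- Grade 3 fracture from a fall, Cycle 2 on time: not a DLT, because the exception applies.
- The same fracture, Cycle 2 given 10 days late: a DLT.
- Grade 1 infection caught at home, Cycle 2 given 8 days late: a DLT.
- Grade 4 event with clear evidence of another cause, no delay: not a DLT.

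Such events add the same background rate at every dose. With at most 12 subjects in cohorts of 2, the model cannot tell that background from toxicity. It moves toward lower doses or toward the early stopping rule.

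**Working it through.** **Text.** In Section 8.0 the exception belongs to the sentence before the delay rule, and the delay rule is introduced as an addition. In Section 5.2.1.2 the rule stands alone. No section attaches attribution to it.

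**Inputs from Section 8.0.** Three L-NMMA levels; start at level 0; cohorts of 2; maximum 12 subjects; normal prior on α with mean 0 and variance 2; working models (0.05, 0.10, 0.15), (0.15, 0.275, 0.40) and (0.40, 0.50, 0.60); no skipping of untried doses; stop if Pr(toxicity at level -1 > 0.25 | data) > 0.80.

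**Assumptions.** Power form, p_i raised to exp(α); equal prior model weights; posterior-mean estimates averaged over models; target 0.25, the lower end of the stated 0.25 to 0.30; free de-escalation. The requirement of 6 subjects at the MTD is not applied. All cohort outcome paths are enumerated exactly.

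**Reproducing Table 9 (no unrelated events).** No dose, Scenarios 1 to 5: 0.029, 0.096, 0.201, 0.307, 0.766, against 0.03, 0.10, 0.20, 0.29, 0.75. Numbers treated agree within 0.3. Selection percentages do not reproduce: the highest dose is chosen in 82% against 77% in Scenario 1, and in 54% against 46% in Scenario 2. An effective target of 0.23 brings all selection figures within about 2 points. The figures below therefore show direction and approximate size only.

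**Adding unrelated delays.** Let u be the chance that a subject has an unrelated AE that delays Cycle 2 by more than 7 days. The documents do not give u; it is assumed equal at all doses. The observed DLT rate is 1 - (1 - p)(1 - u). For example, with p = 0.15 and u = 0.05: 1 - 0.85 × 0.95 = 0.1925.

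Chance of at least one such event in 12 subjects, 1 - (1 - u)^12: 11%, 22%, 46% and 72% for u = 1, 2, 5 and 10%.

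| u | 0 | 1% | 2% | 5% | 10% |
|---|---|---|---|---|---|
| Scenario 1, highest dose selected | 82% | 79% | 76% | 67% | 52% |
| Scenario 1, no dose | 3% | 4% | 5% | 7% | 14% |
| Scenario 2, highest dose selected | 54% | 51% | 49% | 41% | 29% |
| Scenario 2, no dose | 10% | 11% | 12% | 16% | 25% |

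Scenario 3 (true rate 0.35 at the highest dose), for u = 0/2/5/10%: highest dose 29/25/21/14%; no dose 20/23/28/38%. Level 0, whose true rate is 0.25, also loses: 32/30/28/24% in a variant with one-level de-escalation and the final choice limited to doses already tried.

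**Sensitivity to the target.** Scenario 1, highest dose, u = 0/2/5/10%: 76/70/60/44% at 0.23 and 91/88/81/68% at 0.30. The direction is the same.

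**One event in the first cohort.** With one DLT in two subjects at level 0, the estimates are 0.39, 0.48 and 0.56. Level -1 is closest to 0.25, so the next cohort goes there. The chance that the first cohort contains at least one unrelated event is 1 - (1 - u)^2: 2.0%, 4.0%, 9.8% and 19.0% for u = 1, 2, 5 and 10%.

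**The case against.** The best defence is that attribution is implied. Section 3.1 defines DLTs only with the exception. In Section 8.0 the delay sentence leads into a list in which some items require relatedness. In Section 5.2.1.2 the next sentence limits later-cycle interruptions to those caused by toxicity, which suggests that the Cycle 1 rule has the same scope. This shows what the authors may have meant, but it does not close the gap. Section 3.1 defers to Section 8.0, and Section 5.2.1.2 states the rule in full with no list and without the toxicity qualifier. At the least, two readers could score the same event differently.

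The second defence is that an attribution-free criterion is a deliberate safeguard in a small open-label trial where attribution can be wrong. This stands in part. The error is conservative, and in Scenario 3 it reduces selection of the over-toxic highest dose. The price is more trials ending with no dose and less selection of the dose at 0.25. The plan does not present the omission as a choice, and it trusts the same judgement elsewhere in the definition.

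Third, the rate is assumed, and progression of the studied cancer, an obvious non-treatment cause of delay, is already excluded. This stands: at 1% the effect is 3 points on highest-dose selection in Scenarios 1 and 2.

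A reader might infer that the trial will select too low a dose, or that the gap from Table 9 shows an error in the table. Neither is supported: the first needs a rate the documents do not give, and the second needs software settings they do not give.

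**Conclusion.** The concern holds for the text. As written, the delay criterion scores AEs clearly unrelated to treatment as DLTs, at any grade, while the base definition exempts more severe unrelated events. The bias runs toward lower doses and toward stopping with no dose. In Scenario 1 it costs about 3 points of highest-dose selection if 1% of subjects have such a delay, 6 at 2%, 15 at 5% and 30 at 10%. These sizes rest on the assumed rate and on a reconstruction that matches Table 9 for no-dose stops but not for dose selection. The point should be corrected because the DLT is the input to the primary endpoint and the correction is cheap. It does not invalidate the design.

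**What to change.** Reconcile Sections 3.1, 5.2.1.2, 5.6 and 8.0 on whether attribution applies to the delay criterion when DLTs are scored for the CRM. For that scoring, attach to the delay clause the same clear-alternative-evidence exception that the base definition uses. Uncertain cases then still count as DLTs. Report unrelated delays separately, by dose level, from the relatedness already recorded under Section 7.2.

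This changes event scoring only. Whether a subject with an unrelated delay is discontinued under Section 5.6 is a separate clinical rule for the sponsor to reconcile; no change to it is proposed here.

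The cost is one clause, with matching wording where the rule recurs, and no new data. The small downside is that open-label investigators judge attribution, as they already do for the rest of the DLT definition.

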The study will utilize the sequential CRM for two-dimensional dose finding method of Yuan and Yin,⁶⁷ a method based entirely on a Bayesian decision framework. The trial is designed to investigate the combination at one dose level of pembrolizumab (200 mg IV Q3W) and 3 dose levels of L-NMMA (12.5, 15.0, and 20.0 mg/kg). The starting dose will be pembrolizumab at 200 mg IV Q3W and L-NMMA at 15.0 mg/kg. The trial will be comprised of 12 subjects and will utilize a standard Bayesian model averaging CRM approach to determine the appropriate dose of L-NMMA. A cohort size of 2 will be used.

The study was designed and will be conducted using Bayesian model averaging CRM software developed by the Biostatistics Department of the University of Texas M. D. Anderson Cancer Center (<https://biostatistics.mdanderson.org/SoftwareDownload/>).^{68,69} The software assumes the probability of toxicity at dose i (π_i) is modeled as $\pi_i = p_i \times \exp(\alpha)$ where p_i is a constant and α is distributed a priori as a normal random variable with mean 0 and variance 2. The software requires the investigator to specify the prior median probability of toxicity at each of the 3 doses of L-NMMA under consideration (s_i , $i = 1, 2, 3$). The CRM model assumes that toxicity is a monotonic increasing function with dose and thus, the s_i values may not decrease as i increases. The values p_i in the probability model are selected so that $E[p_i \times \exp(\alpha)] = s_i$. After the first cohort, each successive cohort is given the dose whose posterior probability of toxicity given the data collected thus far is closest to the target toxicity (the software does not allow an untried dose to be skipped). Thus as information accumulates, the model is continually updated *posteriorly* and decisions are made on the *posterior* distribution. As a result, no data is lost and

there is the assurance that the decision to increase or decrease the dose level is consistently reassessed as more information becomes available. For a dose level to be chosen as the MTD, at least 6 subjects must have received said dose.

Table 8. L-NMMA Dose Escalation

Dose Level	L-NMMA (mg/kg)
-1	12.5
0	15.0
1	20.0

The target toxicity probability will be 0.25 to 0.30 and a maximum of 12 subjects will be treated. The first cohort of subjects will be treated at dose level 0. As an extra measure of safety, the trial will be stopped early if the lowest dose level is unacceptably toxic, formally if

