$$P_r\{p_{-1} \times e^{\alpha} > 0.25 | data\} > 0.80.$$

The Bayesian model averaging CRM will be implemented using the following three toxicity probability sets: 1) $(p_{-1}, p_0, p_1) = (0.05, 0.10, 0.15)$; 2) $(p_{-1}, p_0, p_1) = (0.15, 0.275, 0.40)$; and 3) $(p_{-1}, p_0, p_1) = (0.40, 0.50, 0.60)$. Operating characteristics of the design under five dose-toxicity scenarios are tabulated below.

Table 9. Phase Ib Design Operating Characteristics (optimal decisions are given in boldface type)

Scenario	Study Parameter	Dose Level			None
		-1	0	1	
1	Prob[toxicity]	0.05	0.10	0.15	0.03
	% Selected	0.03	0.18	0.77	
	# treated	1.0	3.3	7.5	
2	Prob[toxicity]	0.10	0.175	0.25	0.10
	% Selected	0.13	0.32	0.46	
	# treated	2.1	3.9	5.2	

3	Prob[toxicity]	0.15	0.25	0.35	0.20
	% Selected	0.24	0.34	0.22	
	# treated	2.9	4.0	3.5	
4	Prob[toxicity]	0.20	0.30	0.40	0.29
	% Selected	0.30	0.27	0.13	
	# treated	3.2	3.8	2.7	
5	Prob[toxicity]	0.40	0.50	0.60	0.75
	% Selected	0.17	0.05	0.01	
	# treated	2.8	2.6	0.8	

Under Scenario 5 in which all dose levels are too toxic, the estimated probability of finding no acceptable dose is 0.75 with the trial design choosing a dose with 40% toxicity 17% of the time. Scenario 1 represents a setting in which none of the doses is too toxic. For this scenario, the design would chose the highest dose as the MTD 77% of the time.

Data management. CRFs will be designed and utilized to capture all patient data. An electronic database will be designed to store patient CRFs. Data quality control will be performed regularly by the research coordinator to ensure timely, accurate, and complete patient data collection as well as protocol compliance. Queries will be generated and resolved prior to the generation of interim and final summary reports.

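### Section 8.0 writes the CRM model and safety stopping rule as p × exp(α), which is not a probability and is not the model behind Table 9; coded literally, the rule stops less often than stated

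*Combined protocol and SAP*

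**What the plan says.** Section 8.0 uses one expression in three places.

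- **Model.** The toxicity probability at dose i "is modeled as $\pi_i = p_i \times \exp(\alpha)$ where p_i is a constant". The prior for α is normal, centred at 0, with a variance of 2.
- **Calibration.** The investigator is to "specify the prior median probability of toxicity at each of the 3 doses", denoted s_i. Then "The values p_i in the probability model are selected so that" the expectation of p_i × exp(α) equals s_i.
- **Stopping rule.** As a safety measure, "the trial will be stopped early if the lowest dose level is unacceptably toxic". The criterion given for this is "P_r\{p_{-1} \times e^{\alpha} > 0.25 | data\} > 0.80".

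The section gives three toxicity sets for levels −1, 0 and 1: (0.05, 0.10, 0.15), (0.15, 0.275, 0.40) and (0.40, 0.50, 0.60). It names Bayesian model averaging CRM software for both design and conduct. Table 9 reports how often no dose is selected: 0.03, 0.10, 0.20, 0.29 and 0.75 in Scenarios 1 to 5.

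**The concern.** A constant times the exponential of an unrestricted normal variable can exceed 1, so it cannot serve as a toxicity probability without a cap or truncation, and none is stated. The usual one-parameter CRM curve raises the constant to the power exp(α). The two forms also move in opposite directions: as α rises, p^exp(α) falls and p × exp(α) rises.

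This matters because the affected formula is the trial's formal safety rule. If Table 9 came from a different model, the protocol states a rule and a performance that do not belong together. Anyone who programs or audits the rule from the text would then get a different rule from the one whose performance is reported.

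**Working it through.** **Inputs.** From Section 8.0: the prior on α, the three sets, the 0.25 and 0.80 stopping limits, cohorts of 2, a maximum of 12 subjects, a start at level 0, assignment to the dose closest to target, and no skipping of an untried dose. Assumed: equal prior weights for the sets (none are stated) and an assignment target of 0.25 (the text gives 0.25 to 0.30). The written form also needs a convention to keep it at or below 1. I capped π at 1, and as a variant truncated the prior.

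**1. Is the product a probability?** Pr(p × e^α > 1) = Pr(α > −ln p) = 1 − Φ(−ln p / √2). For p = 0.40, −ln p = 0.916, and 0.916/1.414 = 0.648, which gives 0.259.

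| Set | Level −1 | Level 0 | Level 1 |
|---|---|---|---|
| 1 | 1.7% | 5.2% | 9.0% |
| 2 | 9% | 18% | 26% |
| 3 | 25.9% | 31.2% | 35.9% |

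The prior mean is p × e^(2/2) = 2.718p. For set 3 this is 1.09, 1.36 and 1.63, all above 1.

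**2. Which form reproduces Table 9?** I enumerated every outcome path (six cohorts of 2) exactly, applying the stopping rule after each cohort. Probability that no dose is selected:

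| Scenario | Table 9 | Power form p^exp(α) | Written form, capped at 1 |
|---|---|---|---|
| 1 | 0.03 | 0.03 | 0.01 |
| 2 | 0.10 | 0.10 | 0.04 |
| 3 | 0.20 | 0.20 | 0.08 |
| 4 | 0.29 | 0.31 | 0.14 |
| 5 | 0.75 | 0.77 | 0.54 |

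Numbers treated under the power form lie within 0.1 of every Table 9 cell (Scenario 5: 2.9/2.6/0.8 against 2.8/2.6/0.8). The capped written form puts 4.2 subjects at level −1 in Scenario 5, against 2.8. With a truncated prior it stops in 0.47 of Scenario 5 trials.

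Sensitivity to the target: the same enumeration at 0.30 gives 0.03/0.09/0.20/0.30/0.75 for the power form and 0.01/0.03/0.08/0.13/0.51 for the capped written form. Over the targets, final-selection rules and last-cohort stopping conventions tried, the written form's worst error in this column was never below 21 points (capped) or 28 points (truncated). The power form's was under 1 point at best.

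**3. What does the stopping statistic do?**

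| Data | Power form throughout | Written form throughout, capped |
|---|---|---|
| 2/2 DLTs at level 0 | 0.944, stop | 0.925, stop |
| 0/12 DLTs (all at level 1) | 0.000, continue | 0.000, continue |

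With a truncated prior the written form gives 0.69 after 2/2 DLTs (continue) and 0.94 after 4/4 (stop).

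A mixed calculation, taking the posterior of α from the power-form CRM and inserting it into the written product, gives 0.114 after 2/2 DLTs and 0.637 after 0/12. Its maximum over all paths is 0.637, below 0.80.

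**4. Median or mean?** Under the written form the median of p × e^α is p × e^0 = p and the mean is 2.72p, so s_i cannot be both. If the three sets are the p_i, as labelled, the calibration makes s_i for set 3 exceed 1. Under the power form the median of p^exp(α) is p^exp(0) = p, which fits the word median.

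**The case against.** The strongest answer is that conduct is probably unaffected. The named software is to run the trial, and the close match of the power form to Table 9 suggests that it applies that form. Live decisions would then agree with the table, and the error lies in the written description. That stands as far as the documents allow, but the software's own rule is not shown in them.

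A reader might infer that the written stopping formula would never stop a toxic trial. The documents do not support this. Model and rule use the same product, so they agree in direction, and fitted together the capped form makes the same decision as the power form in both examples above. The rule fails to fire only in the mixed calculation, which nothing in Section 8.0 specifies. That mixture is a hazard for a hand check or re-coding that takes α from the software and the statistic from the text. The opposite direction of the two forms is likewise not an error in itself, because the prior on α is symmetric.

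Other limits are fair. The excess over 1 is large mainly in set 3 and small in set 1. The match to Table 9 rests on assumed weights and target and is close rather than exact. A superscript lost in conversion cannot be excluded without the source file, but an explicit multiplication sign in all three formulas makes that unlikely.

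**Conclusion.** Wrong as written. The product form is not a probability model and contradicts the operating characteristics in the same section. Coded literally with a cap at 1, the safety rule is weaker than Table 9 reports: 0.54 against 0.75 in Scenario 5, and 0.14 against 0.29 in Scenario 4. It does not fail altogether. The power form reproduces the no-dose column to within 2 points.

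These figures assume equal set weights and a 0.25 target; moving the target to 0.30 does not change the conclusion. The written-form figures also depend on the cap, and truncation lowers Scenario 5 to 0.47. The median and mean conflict needs no assumption beyond the stated prior. Nothing here shows that the trial has been or will be run on the wrong rule.

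**What to change.** Make three corrections in Section 8.0:

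1. Model: π_i = p_i^exp(α).
2. Stopping rule: Pr{p_{-1}^exp(α) > 0.25 | data} > 0.80, stated to be averaged over the three models. The limits 0.25 and 0.80 stay as they are.
3. Replace the expectation sentence with a statement that p_i is the prior median toxicity probability at dose i.

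Before issuing the change, confirm against the software documentation that these are the formulas it applies, and check the source file for a lost superscript. Stating the set weights and the single assignment target in the same edit would let a reader reproduce Table 9.

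The cost is three formula edits and one check. The software and Table 9 do not change.

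### Section 8.0 prints the CRM model and the stopping rule as p × exp(α), which is not a probability model and does not match Table 9; the power form, model weights and point target should be stated

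*Combined protocol and SAP*

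**What the plan says.** Section 8.0 gives the same expression in three places.

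- Model: toxicity at dose i is "modeled as $\pi_i = p_i \times \exp(\alpha)$ where p_i is a constant". The stated prior for α is normal, centred at 0, with a variance of 2.
- Calibration: the constants "are selected so that $E[p_i \times \exp(\alpha)] = s_i", although s_i has just been introduced as a median: "The software requires the investigator to specify the prior median probability of toxicity at each of the 3 doses of L-NMMA under consideration".
- Stopping rule: the trial stops early if "P_r\{p_{-1} \times e^{\alpha} > 0.25 | data\} > 0.80".

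The section then says: "The Bayesian model averaging CRM will be implemented using the following three toxicity probability sets". They are (0.05, 0.10, 0.15), (0.15, 0.275, 0.40) and (0.40, 0.50, 0.60). No prior weights are given for the sets, the displayed stopping rule has one p and one α, and the target is a range, 0.25 to 0.30. Section 8.0 also states that named model-averaging CRM software was used for the design and will be used for the conduct of the trial. Table 9 reports the operating characteristics.

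**The concern.** A constant multiplied by exp(α), with α on the whole real line, can take any positive value. No cap or truncation is stated, so the printed expression has no valid binomial likelihood and cannot be run without an added assumption. This expression is the only written specification of dose assignment, of the formal toxicity stop and of MTD selection. If it differs from the model behind Table 9, the text and the reported safety properties describe different designs. A statistician or monitor who checked a decision from the text could reach the opposite answer from the software.

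**Working it through.** **Inputs (all Section 8.0).** α ~ N(0, 2), so SD = √2 = 1.414; the three sets above; start at level 0 (15.0 mg/kg); cohorts of 2, maximum 12, hence 6 cohorts; stop cut-off 0.80; no skipping of an untried dose.

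**Assumptions.** Prior weight 1/3 per set, point target 0.25, and dose choice and stopping based on model-averaged posterior quantities. The six-subject condition for naming an MTD is not applied. (With it, the power form gives None = 0.23 in Scenario 1, against 0.03 stated.) All trial paths were enumerated exactly.

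**Step 1: is the product a probability?** Pr(p·e^α > 1) = 1 − Φ(ln(1/p)/√2).
- p = 0.40: ln(2.5)/1.414 = 0.648, giving 0.26.
- p = 0.50: 0.693/1.414 = 0.490, giving 0.31.
- p = 0.60: 0.511/1.414 = 0.361, giving 0.36.
- Set 2 gives 0.09/0.18/0.26; set 1 gives 0.017/0.052/0.09.

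E[e^α] = exp(2/2) = 2.718, so the prior means for set 3 are 0.40 × 2.718 = 1.09, 0.50 × 2.718 = 1.36 and 0.60 × 2.718 = 1.63.

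**Step 2: which form produced Table 9?** Probability that no dose is selected (None):

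| Scenario | Table 9 | Power form p^exp(α) | Product, capped at 1 | Product, α truncated so all values < 1 |
|---|---|---|---|---|
| 1 | 0.03 | 0.029 | 0.011 | 0.000 |
| 2 | 0.10 | 0.096 | 0.036 | 0.005 |
| 3 | 0.20 | 0.201 | 0.082 | 0.023 |
| 4 | 0.29 | 0.307 | 0.136 | 0.061 |
| 5 | 0.75 | 0.766 | 0.544 | 0.471 |

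Numbers treated under the power form agree with Table 9 to about 0.1 in every cell (Scenario 5: 2.86/2.63/0.78 against 2.8/2.6/0.8). Selection percentages do not all agree. Scenario 5 is close (0.179/0.043/0.012 against 0.17/0.05/0.01), but Scenario 2 gives 0.24 against 0.32 at level 0 and 0.54 against 0.46 at level 1. A target near 0.23 brings every selection cell within 2 points, but then numbers treated miss by up to 0.34.

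**Step 3: what the printed product would do.** In Scenario 5 (true toxicity 0.40/0.50/0.60), with the capped result first and the truncated result in brackets:
- None: 0.54 (0.47), against 0.75 stated.
- Selection of the 40%-toxic lowest dose: 0.36 (0.43), against 0.17.
- Expected subjects at that dose: 4.2 (6.0), against 2.8.

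With targets of 0.275 to 0.30, or with the listed values read as s_i and p_i = s_i/2.718, None is 0.42 to 0.53.

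**Step 4: one decision.** Data: 1/2 DLTs at 15.0 mg/kg, then 1/2 at 12.5 mg/kg. Under the power form the three sets give Pr(toxicity at 12.5 > 0.25) = 0.760, 0.776 and 0.852. With equal prior weights the posterior weights are 0.262, 0.332 and 0.406:

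0.262 × 0.760 + 0.332 × 0.776 + 0.406 × 0.852 = 0.199 + 0.258 + 0.346 = 0.803 (0.802 to 0.803, depending on the numerical grid): stop.

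The product gives 0.54 (capped) or 0.52 (truncated): continue. Prior weights 0.4/0.3/0.3 in the power form give posterior weights 0.321, 0.305 and 0.373, and 0.244 + 0.237 + 0.318 = 0.799: continue. This path has probability [2(0.15)(0.85)] × [2(0.25)(0.75)] = 0.10 in Scenario 3, 0.32 × 0.42 = 0.13 in Scenario 4 and 0.48 × 0.50 = 0.24 in Scenario 5.

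**Step 5: calibration.** Under the power form, α = 0 gives the prior median, which is p_i. The mean is different: E[p^exp(α)] = 0.187 at p = 0.05, 0.231 at 0.10, 0.266 at 0.15 and 0.540 at 0.60. Choosing p_i so that the mean equals the listed values gives None = 0.013/0.049/0.118/0.200/0.669, which does not match Table 9. Treating the listed values as prior medians does.

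**The case against.** The strongest reply is that the formula describes a package and is not a specification to be programmed. The design and the conduct both use that software, and Table 9 shows that the software holds a valid model. This stands, and it limits the point. A reader might infer that the trial will deliver less protection than Table 9 states; the documents do not support that.

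Second, the figures for the printed product depend on a cap or truncation that appears nowhere in the protocol. That is true, so they are illustrations. Under model averaging, Scenario 5 None stayed between 0.42 and 0.54 in every variant tried. It reached 0.67 to 0.71 only when the single best model replaced averaging, which the protocol does not specify.

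Third, a reader might take the match as proof of equal weights. It is not: 0.3/0.3/0.4 gives None = 0.029/0.097/0.203/0.312/0.776, and 0.25/0.25/0.5 stays within 0.034 of Table 9. The stop in Step 4 is also a near tie. It shows that the unstated weights can decide a stop, which is a separate matter from the multiplication sign.

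Fourth, the signs could come from conversion of the PDF. This is unlikely, because the product appears in three formulas and the displayed rule keeps α as a superscript of e. It is not excluded, since one program read all three.

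**Conclusion.** As printed, the model, its calibration and the stopping rule are wrong. The product is not a probability and does not generate Table 9. The power form accounts for the None column (within 0.02) and the numbers treated (within about 0.1) under equal weights and target 0.25, but not for every selection cell (gaps up to 8 points), so the exact set-up is not recoverable from the text. The loss of protection, with Scenario 5 None falling from 0.75 to about 0.54 or 0.47, is conditional: it arises only if someone codes or verifies decisions from Section 8.0 and handles values above 1 in one of the ways assumed here. The defect lies in the written decision rule; no fault in the software is shown.

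**What to change.** 1. Print π_i = p_i^exp(α) in the model and p_{-1}^exp(α) in the stopping rule.
2. Rewrite the calibration sentence so that it agrees with the prior median: under the power form s_i = p_i. Do not simply put the power form inside the expectation, because that mean is not the median.
3. Write the stopping rule as the model-averaged posterior probability, Σ_k w_k Pr{p_{k,-1}^exp(α) > 0.25 | data, set k} > 0.80, where w_k are the posterior model weights. State the prior model weights and the single point target actually set in the software, as confirmed by the sponsor. Equal weights should not be written in by inference.
4. Confirm that the software set-up reproduces Table 9, including the selection percentages, before the next dose decision. Check the source page to rule out a conversion artefact.

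The cost is a wording amendment to Section 8.0 and one software check. No patients are added and the design does not change.
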